In the past decades, the scientific focus regarding calcaneus fractures was the choice of operative or non-operative treatment modality. Although the evidence is ambiguous [1], recent meta-analyses suggest that operative therapy is associated with a higher likelihood to resume pre-injury work, to reach a higher level of physical function and fewer problems when wearing shoes. However, non-operative therapy has significantly less complications and infections [2,3]. Typically, aftercare includes non- or partial weight bearing, but protocols are different and often not very specific. In fact, there are no studies published comparing different procedures or special supporting devices. Recently, a heel-unloading orthosis ('Settner shoe' [4]) was introduced in aftercare for calcaneus fractures, allowing walking by shifting the load to the middle- and forefoot. This orthosis does not only enable early mobilization of patients suffering one-sided fractures, but also permits going following two-sided fractures, avoiding the otherwise necessary wheel-chair mobilization. The 'Settner shoe' can be applied in non-operative therapy and following operations. Specifically in calcaneus fractures, early regain of physical activity has been highlighted as one of the key factors for quality of life and the ability to return to work [2,3]. Thus, we hypothesize that mobilization with the 'Settner shoe' results in higher physical activity within the first 3 months and secondly improves ability to return to work in calcaneus fracture patients aged 18-60 years. Further outcome criteria are the American Orthopaedic Foot and Ankle Society's (AOFAS) ankle-hindfoot assessment, a 3-dimensional gait analysis, and the EQ-5D-3L questionnaire. It is the first trial applying a standardized aftercare in patients suffering from calcaneus fractures aiming to improve the non-operative part of treatment. Furthermore, the trial clarifies, whether the economical effort for the equipment acquisition is scientifically justified.

Objectives

We hypothesize that mobilization with the 'Settner shoe' results in higher physical activity within the first 3 months after calcaneus fractures.

Research questions

Does the application of a heel-unloading orthosis ('Settner shoe') independent of operative or non-operative therapy of a calcaneus fracture improve:

- 1.) the physical activity (active minutes per day)?
- 2.) the quality of life (EQ-5D-3L)?
- 3.) the foot function (AOFAS)?
- 4.) the time necessary for return to work in patients between 18 and 60 years?

Trial design

The study design is a parallel group, randomized controlled trial with open allocation including all patients with calcaneus fractures independent of kind of initial therapy.

Methods: Participants, interventions, and outcomes

Study setting

All patients treated for calcaneus fracture (DS920* 'Fraktur af hælben' according to the Danish SKS-browser) at the University Hospital Odense are prospectively screened for eligibility and included in the trial, if they fulfil the inclusion criteria as listed below. The follow-up period is 6 months.

Eligibility criteria

In Denmark, the treatment of calcaneus fractures is regarded as highly specialized, wherefore both decision-making and operations are done for the whole Region of Southern Denmark in the Department of Orthopaedics and Traumatology at the University Hospital Odense. Therefore, patients are screened by consultants of the local trauma section.

Inclusion criteria:

- Fracture of the calcaneus, which is classifiable according to the Sanders' classification (excludes avulsion fractures)
- Being able to understand Danish or English and answer the questionnaires
- Informed consent
- Age between 18 and 65 years

Exclusion criteria:

- Pathological fractures
- Immature skeletal system
- Other fractures with influence on weight-bearing
- A soft-tissue situation not allowing the equipment with a 'Settner shoe' within 3 weeks after treatment (either decision-making for non-operative therapy or open reduction and internal fixation)

Acquiring patient consent

The participants will be introduced to the study by the medical personnel in a room, where they will not be disturbed. It will be assured that patients are allowed (if they wish) to be introduced to the study accompanied by a family member or any other person(s) selected by the patient. Patients will be given an oral overview of the purpose of the study, a participant information document describing the study and potential risk together with a patient consent form, which the patients will sign if they decide to participate in the study. The patient can resign from participating in the study without giving a reason and without any consequences. Patients are included after the operation or after decision for non-operative therapy, but before discharge.

Interventions

After operation or decision for non-operative therapy, the schedule for the 2 groups are defined as follows:

Group 1 (treatment without 'Settner shoe'):

- mobilization without weight bearing for 6 weeks starting with the day of either decision-making for non-operative therapy or open reduction and internal fixation, if needed a cast or another kind of orthosis as a Static Walker are applied, then 4 weeks 15-20 kg, 2 weeks 35-45 kg, after that transition to full-weight bearing (always only if possible)

- X-ray after 6 and 12 weeks; depending on the results, the schedule for weight bearing may be adjusted to the need in case of delayed healing or complications related to implants

Group 2 (treatment with 'Settner shoe'):

- mobilization with the custom-made heel-unloading orthosis ('Settner shoe') without pads for 6 weeks, then 2 weeks one pad, 2 weeks 2 pads, 2 weeks 3 pads, after that full-weight bearing without any support (always only if possible)
- X-ray after 6 and 12 weeks; depending on the results, the schedule for weight bearing may be adjusted to the need in case of delayed healing or complications related to implants

The patients of both groups are informed about the aftercare at the time point of inclusion.

Outcomes

Primary outcome criterion

The number of active minutes per day following 3 months (time point 2) is primary outcome criterion.

Secondary outcome criteria

- active minutes per day at time point 1
- portion of highly active periods per day at time point 1 and 2
- the EuroQol 5D-3L questionnaire following 3 months (time point 2)

Explorative outcome criteria

- AOFAS
- 3-dimensional gait analysis
- time point of return to work of patients between 18 and 60 years
- range of motion (ROM)
- Pro- and supination (percent of healthy side or assumed normal mobility) are analyzed.
- pain
- The evaluation includes the medication and a visual-analogue scale (VAS).
- comparison between patients with and without operation

Patient characteristics beside outcome criteria

Epidemiology

- age
- sex
- body mass index
- ASA (American Society of Anesthesiologists) physical status classification system

Injury characteristics

- classification according to Sanders (figure 4)
- classification of open/closed tissue damage (table 1)
- polytrauma (ISS \geq 16, multiple injuries, monitrauma)
- indication for operation (dislocation, broadening, flattening of Böhler angle etc.) or conservative therapy (comorbidity, smoking etc.)

- the time between the fracture occurred and operation or decision making for non-operative therapy

[figure not shown]
Healing and treatment characteristics

- bone healing after 3 months: union or delayed healing
The decision is made based on conventional radiographs including the clinical description of complains.
- weight bearing after 3 months
Is it possible or not?
- hindfoot axis (varus/valgus-deformity, Böhler angle, subtalar osteoarthritis)
The decision is made based on conventional radiographs and a clinical evaluation.
- type of operation (approach, fixation method, graft)

Complications

- infection (I)
- deep venous thrombosis (DVT)
- nerve paresis/palsy/disturbed sensibility (N)
- subtalar posttraumatic osteoarthritis (PTOA)
- subtalar instability (SI)
- local mechanical irritation by plate/screws (LI)
- wound irritations (WI) as superficial healing problems or skin edge necrosis
- irritations associated to the use of the custom-made heel-unloading orthosis ('Settner shoe')

Participant timeline

The clinical and radiological controls correlate with the usual guidelines for treating calcaneus fractures at the Odense University Hospital.

Sample size and power analysis

The sample size calculation was based on a 33% difference in activity, correlating with a clinical relevant difference. Setting the power to 80% and the 2-sided confidence interval to 95% the calculation according to the method of Fleiss with continuity correction resulted in 25 patients per group.

Recruitment

All consultants of the trauma section of the Department of Orthopaedics and Traumatology at the University Hospital Odense are involved in the recruitment process of the study.

Methods: Assignment of interventions (for controlled trials)

Allocation

In the period between treatment (either decision-making for non-operative therapy or open reduction and internal fixation) and consolidation of the soft-tissue situation, the patients are randomized for the aftercare with or without the custom-made heel-unloading orthosis ('Settner shoe'). As soon as the soft-tissue situation allows the adjustment, the patients are referred to an orthopaedic shoemaker, who equips the patient accordingly. The randomization is done using the tool provided by OPEN.

Blinding (masking)

The allocation is not blinded, because it will be obvious to the patient, whether a special shoe is worn or not. Furthermore, the treating trauma surgeon needs to initiate the prescription.

Methods: Data collection, management, and analysis

Management and collection

REDCap™ (Research Electronic Data Capture), a secure application for online surveys and databases, facilitates data management. The University Hospital Odense is an institutional partner of REDCap™, which was especially designed for biomedical research and fulfills all necessary safety features. This is supported by the OPEN initiative (Odense Patient data Explorative Network). REDCap™ used with the OPEN-platform supports also a randomization function, which is used for the study.

Statistical methods

Normally distributed numeric data sets are compared using the paired Student's t-test. Otherwise or in case of non-numeric data, nonparametric tests determine the significance of difference. For correlations, Spearman ρ is calculated. Incidences are compared using the chi square test. Otherwise or in case of non-numeric data, nonparametric tests as the Mann-Whitney U-test for two and the Kruskal-Wallis H-test for multiple variables determine the significance of difference. For correlations, Spearman ρ is calculated.

Methods: Monitoring

Data monitoring

When the study is accepted for OPEN, a data manager will automatically be assigned to the study. The data manager will support the data coherence. Furthermore, a yearly data monitoring will be done by a study nurse, who is assigned to the project.

Harms

Any adverse or severe adverse events will be registered during the trial. Expected are especially local mechanical irritations, which are listed in the chapter for registration of patient characteristics beside outcome criteria.

Ethics and dissemination

Ethics

The study needs to be approved by the ethical board of the Region of Southern Denmark (<https://komite.regionssyddanmark.dk/wm258128>).

Patient law/privacy

All data collected from patients are protected by the Act on Processing of Personal Data and Health Act according to Danish Data Protection Agency. The project will be reported to Datatilsynet (under "Regionens Paraply 2012-58-0018"). The database is established with OPEN, however, other possible related files are stored in a secure Sharepoint (<https://secure.regionssyddanmark.dk/projektrum/ProTibExPla/SitePages/Startside.aspx>).

Publication

Reporting will be conducted according to Consolidated Standards of Reporting Trials (CONSORT guidelines (<http://www.consort-statement.org/>) and published in a peer reviewed journal.

Appendices

Measurement of physical activity

For monitoring of activity, the patients are equipped with a Misfit™ Shine (Burlingame, CA, USA) at the ankle and an Axivity™ AX3 (Newcastle upon Tyne, UK) at the lateral femur of the unaffected side. If there is a fracture at both sides, the trackers are attached to the side with the less complicated fracture. The wear time is 7 days. At day 7±14 (discharge) and after 3±0.5 months patients are equipped, and activity signals are analyzed by calculating the mean of all acquired 24-hour-data during these two periods. Regarding the Misfit™ Shine, only the number of registered steps is recorded. Regarding the Axivity™ AX3, the portion of highly active periods per day and the number of active minutes, correlating with walking activity, have shown to be most discriminating in the preliminary validation study. Therefore, these parameters are selected. Reliability is checked using a wear-time analysis based on change of signal vector magnitudes and temperature monitoring.

Correlating with these two data points, the EuroQol 5D-3L questionnaire [5] and the AOFAS [6] are monitored.

Classification

Classification of calcaneus fractures according to Sanders

[figure not shown]

Figure 3: Axial load is necessary for calcaneus fractures, which should be treated with a heel-unloading 'Settner shoe'.

[figure not shown]

Figure 4: The fracture classification according to Sanders can group the calcaneus fractures that occur following axial load [7].

Classification of open fractures according to Gustilo-Anderson

| Gustilo Grade | Definition |
|---------------|--|
| I | Open fracture, clean wound, wound <1 cm in length |
| II | Open fracture, wound > 1 cm but < 10 cm in length without extensive soft-tissue damage, flaps, avulsions |
| III | Open fracture with extensive soft-tissue laceration (>10 cm), damage, or loss or an open segmental fracture. This type also includes open fractures caused by farm injuries, fractures requiring vascular repair, or fractures that have been open for 8 hr prior to treatment |
| IIIA | Type III fracture with adequate periosteal coverage of the fracture bone despite the extensive soft-tissue laceration or damage |
| IIIB | Type III fracture with extensive soft-tissue loss and periosteal stripping and bone damage. Usually associated with massive contamination. Will often need further soft-tissue coverage procedure (i.e. free or rotational flap) |
| IIIC | Type III fracture associated with an arterial injury requiring repair, irrespective of degree of soft-tissue injury. |

Table 1: The classification of open fractures according to Gustilo-Anderson [8].

Orthosis

The heel-unloading orthosis ('Settner shoe' [4]) can be used for conservative treatment and aftercare following surgery. It needs to be assembled out of pre-formed and size-adjusted parts. This is done by an orthopaedic shoemaker. The increase of weight bearing is achieved by pads. The first 6 weeks the shoe is worn without pads. Then, the first pad is applied. Every 2 weeks a further pad is put in the shoe, which is removed after 3 months. Preliminary data suggest that this heel-unloading orthosis reduce days of inability to work.

Figure 1: heel-unloading orthosis ('Settner shoe' [4])

Figure 2: Principle of biomechanical unloading of the heel

3-dimensional gait analysis

All outcome calculations will be based on measurements taken during gait using a 3D Vicon MX movement analysis system with eight cameras operating at 100 Hz (Vicon, Oxford, UK) and two AMTI force-plates (AMTI, OR6-7, Watertown, MA, USA) embedded at floor level, operating at 1,000 Hz. A technician experienced in gait analysis and the Vicon system will attach reflective markers that reflect infrared light according to the Vicon Plug-in-Gait marker set and model [9].

Patient involvement

The Misfit™ Shine worn at the healthy ankle can be coupled with an android or OS X app, which not only provides objective data about patient mobility during early aftercare, but at the same time signals feedback to the patient. By this, the patients themselves can control their postoperatively increasing activity. This includes a scientifically supported evaluation by the study leader at the defined follow-up time points at 6 weeks and 3 months after therapy start. The usual activity data published for healthy people are not comparable to this group, because the physical activity from patients in a rehabilitation process is usually lower. This way, the patient gets trained to interpret the data acquired by the app.

References

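### The exclusion of other fractures can be read to bar two-sided calcaneus fractures that the rest of the plan expects; laterality is neither recorded nor used in the primary comparison, which risks chance imbalance and extra variance, not bias

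*Combined protocol and SAP*

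**What the plan says.** Under Eligibility criteria, the exclusion list bars "Other fractures with influence on weight-bearing". The word 'other' is not defined. The inclusion criterion asks for a Sanders-classifiable calcaneus fracture and sets no limit to one side.

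Four other places bear on two-sided fractures:

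- The introduction says of the orthosis that it "also permits going following two-sided fractures, avoiding the otherwise necessary wheel-chair mobilization".
- Trial design describes a "randomized controlled trial with open allocation including all patients with calcaneus fractures independent of kind of initial therapy".
- The appendix on measurement of physical activity puts the trackers on the unaffected side and adds: "If there is a fracture at both sides, the trackers are attached to the side with the less complicated fracture".
- The exploratory range-of-motion outcome allows for a patient with no sound side for comparison: "Pro- and supination (percent of healthy side or assumed normal mobility) are analyzed".

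The patient, injury, healing and complication lists contain no item for side or for one-sided versus two-sided fracture. The nearest item, on polytrauma and multiple injuries, would not identify a second calcaneus fracture. Allocation names no stratification factor, and Statistical methods describes simple tests with no covariate.

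**The concern.** There are two linked problems.

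The first is who enters. A fracture of the opposite heel is, in plain words, another fracture that affects weight-bearing, so the exclusion can be read to bar the patient. The appendix assumes that the same patient is in the trial. All consultants of the trauma section recruit, and the eligibility text does not settle the question for them.

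The second is what happens once such patients are in. The primary outcome is active minutes per day at 3 months, which the appendix ties to walking. The plan itself links two-sided fracture to walking ability, and its tracker rule means that these patients are measured on a fractured leg rather than a sound one. With about 25 patients per arm, a few patients with lower values can fall unevenly by chance. Without a planned laterality item, the analysis can neither show that nor adjust for it.

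**Working it through.** **Inputs from the documents.** 25 per group, 80% power, two-sided 95%, a 33% difference in activity (Sample size and power analysis). Primary outcome at 3 months (Outcomes), with a measurement window of ±0.5 months (appendix).

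**Inputs that are assumptions.** 3 to 5 two-sided patients among 50 (6-10%). Their active minutes are 30-50% below those of one-sided patients, by the same amount in both arms. The 33% is treated as a relative difference in mean minutes, with the control mean and the one-sided mean on the same scale. The documents state none of these.

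**The plan's own figure.** The Fleiss formula with continuity correction gives 25 per group for 0.67 versus 1.00 (or 0.00 versus 0.33). Without the correction, n = [1.96·√(2·0.835·0.165) + 0.842·√(0.67·0.33)]² / 0.33² ≈ 18.6, rounded up to 19. With it, n = (18.6/4)·[1 + √(1 + 4/(18.6·0.33))]² ≈ 24.3, rounded up to 25. The two rates are assumed, since only their difference is given. The figure is not in dispute here.

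**Implied spread.** For a comparison of means, 25 per group at 80% power implies SD = 0.33 / [(1.96 + 0.842)·√(2/25)] ≈ 0.416 of the mean. The standard error of the difference is 0.416·√(2/25) ≈ 0.118.

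**Chance of an uneven split** (hypergeometric, 50 patients, 25 per arm), for a net imbalance of three or more:

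| Two-sided patients | Splits | Probability |
|---|---|---|
| 3 | 3:0 | 2·C(25,3)/C(50,3) = 0.235 |
| 4 | 4:0 | 2·C(25,4)/C(50,4) = 0.110 |
| 5 | 4:1 or 5:0 | 2·(0.149 + 0.025) = 0.349 |

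**Effect of a net imbalance of three.** Shift = 3 × deficit / 25.

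| | 30% deficit | 50% deficit |
|---|---|---|
| Shift, share of the one-sided mean | 0.036 | 0.060 |
| Shift as share of 0.33 | 11% | 18% |
| Power given the imbalance, against the orthosis | 70% | 63% |
| Power given the imbalance, in its favour | 87% | 91% |
| False-positive rate given the imbalance | 6.1% | 8.0% |

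These are conditional figures. Over all possible randomizations the shifts cancel and the overall type I error stays nominal.

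**Extra variance.** A share q with deficit D adds q(1 − q)D² to the variance. Relative to 0.416² ≈ 0.173:

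- q = 0.06, D = 0.30: 0.0564·0.09 / 0.173 ≈ 3%
- q = 0.10, D = 0.50: 0.09·0.25 / 0.173 ≈ 13%

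If the SD of 0.416 describes one-sided patients only, power with a 10% share is about 78% at a 30% deficit and 75% at 50%. The conditional shifts and the added variance are two views of the same effect and must not be added together.

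**Timing.** Group 1 is scheduled for 6 + 4 + 2 = 12 weeks before the transition to full weight bearing, and group 2 for 6 + 2 + 2 + 2 = 12 weeks. At 3 months both are therefore at or near the end of restricted loading. The window reaches back to 2.5 months, about 11 weeks, so some patients are measured before that point.

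**The case against.** The strongest reply is that the plan, read as a whole, already includes two-sided patients. After an inclusion criterion about the calcaneus, 'other fractures' reads at least as naturally as fractures of other bones, and the design statement, the tracker rule and the range-of-motion wording all fit that reading. Nothing shows that consultants at this single centre would disagree. This stands. A reader might infer that the exclusion removes two-sided fractures, but the documents support only an ambiguity. If the inclusive reading is right, however, the missing laterality item matters more, because these patients do enter.

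A second reply concerns the wheelchair remark. A reader might infer from it that two-sided patients differ sharply on the primary outcome. The remark is made about early mobilization, whereas the primary outcome is at 3 months, when both schedules are ending. It fits time point 1 better. At 3 months a smaller deficit is likely, though the documents do not exclude one.

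Third, a large distortion can be produced on paper. Five such patients, a 4:1 split and near-zero minutes give 3/25 = 12% of the one-sided mean. That requires near-zero activity at 3 months in both arms, although the plan says that these patients can walk in the shoe. If only controls were so inactive, the treatment effect would differ by laterality, and a covariate without an interaction would not address that.

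Fourth, laterality is probably recoverable. Staff must know it to place the trackers, and radiographs exist. So it would be too strong to say that an imbalance could never be seen. What stands is that laterality is not a planned item and no analysis uses it.

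Finally, a covariate turns the plain test into a regression for a subgroup assumed to be 6-10% of patients. That is a real cost, but a small one.

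**Conclusion.** The point holds as an ambiguity to be reconciled and a modest, inexpensive improvement to the analysis. The exclusion wording does not say whether a second calcaneus fracture counts as other, while the rest of the plan implies that two-sided patients are enrolled. For those patients laterality is a plausible prognostic factor and changes where the tracker is worn, but it is neither recorded nor used.

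Under the assumed counts and deficits, a net imbalance of three shifts the arm difference by about 4-6% of the one-sided mean. An imbalance of three or more has a probability of 11-35%, depending on the count. Adjustment would remove added variance worth about 3-13% of the one-sided variance. The true size is unknown, because the documents give neither the number of two-sided patients nor their deficit.

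A reader might infer that the primary result is biased. The documents do not support that: with randomized allocation the harm is chance imbalance and lost precision.

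**What to change.** 1. State explicitly whether a second calcaneus fracture counts as 'other', so that the exclusion agrees with the introduction, Trial design and the tracker rule. If two-sided patients are meant to enter, restricting the exclusion to fractures other than of the calcaneus on either side would do this.
2. Add one-sided / two-sided to the injury characteristics.
3. Pre-specify laterality as a covariate in the between-group primary comparison: active minutes at 3 months regressed on arm and laterality.
4. Pre-specify a sensitivity analysis of the primary outcome in one-sided fractures only. This also covers a possible difference in treatment effect by laterality, which an interaction term could not usefully estimate with only a few two-sided patients.

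The cost is one eligibility line, one REDCap field, one degree of freedom, one extra analysis, and a simple regression in place of the plain two-group test.

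### Does the 3-week soft-tissue exclusion undermine the randomised comparison, given that patients are randomised before shoe fitting is known to be possible?

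*Combined protocol and SAP*

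**What the plan says.** Under Exclusion criteria the protocol lists "A soft-tissue situation not allowing the equipment with a 'Settner shoe' within 3 weeks after treatment", where treatment means either the operation or the decision to treat without one. Study setting says that patients are "prospectively screened for eligibility and included in the trial, if they fulfil the inclusion criteria as listed below", and Eligibility criteria gives the screening to consultants of the trauma section. Acquiring patient consent adds: "Patients are included after the operation or after decision for non-operative therapy, but before discharge".

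Allocation dates randomisation to the interval from treatment to soft-tissue recovery: "consolidation of the soft-tissue situation, the patients are randomized for the aftercare with or without the custom-made heel-unloading orthosis". Fitting comes later: "As soon as the soft-tissue situation allows the adjustment, the patients are referred to an orthopaedic shoemaker, who equips the patient accordingly". Trial design describes a "parallel group, randomized controlled trial with open allocation".

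The appendix Measurement of physical activity sets the two tracker periods: "At day 7±14 (discharge) and after 3±0.5 months patients are equipped". The second supplies the primary outcome, active minutes per day at 3 months.

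Statistical methods lists tests. It names no analysis population and gives no rule for a randomised patient who turns out not to be fittable.

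**The concern.** The criterion looks up to 3 weeks ahead, while randomisation happens inside that window. Whether a patient meets it may therefore become certain only once the arm is known, and the arm is known to everyone. Only shoe-arm patients go to the shoemaker, so a failed fitting would come to light mainly in that arm. If such patients were then treated as ineligible and dropped, while control patients with equally poor soft tissue stayed in, the arms would no longer be comparable on soft-tissue status when 3-month activity is compared. The result would favour the shoe if unfittable patients are less active and count against it if they are more active. With 25 patients per group, a handful of removals could matter.

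**Working it through.** **1. The order of events.** Set side by side, the sections give this sequence: treatment; screening and inclusion before discharge; randomisation before the soft tissue has settled; fitting in the shoe arm once it has; activity measurement at 3 months. An eligibility item applied at the second step and looking 3 weeks ahead is a prediction by the screening consultant. On that reading Exclusion criteria and Allocation agree. Literal confirmation after allocation is possible in principle: 3 weeks is 21 days, and if discharge falls on the nominal day 7 counted from treatment, 21 − 7 = 14 days remain. The day-7 label belongs to the tracker schedule and its starting point is not stated, so the 14 days only illustrate the gap.

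**2. What happens to an unfitted patient as the plan stands.** The only withdrawal described is the patient's own choice (Acquiring patient consent). The 3-month tracker period is scheduled for patients in general, with no condition on wearing the shoe. Complications, including wound problems, are recorded without restriction to one arm. Following the text therefore keeps the patient in the trial, measured and compared by group.

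**3. The plan's own figure.** Sample size and power analysis gives 25 per group from a 33% difference, 80% power, two-sided 5% and the Fleiss method with continuity correction. The group proportions are not stated; 100% against 67% reproduces the figure:

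- Uncorrected n = [1.960 × √(2 × 0.835 × 0.165) + 0.842 × √(0 + 0.67 × 0.33)]² / 0.33² = 18.6, so 19.
- Corrected n = (18.6/4) × [1 + √(1 + 4/(18.6 × 0.33))]² = 24.3, so 25.

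The present point uses only the 25 per group.

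**4. What one-sided removal would do.** The documents give neither the number unfittable nor their activity, so these are assumptions: k of 25 shoe-arm patients removed; unfittable patients less active by δ SD; each control patient unfittable with probability k/25 and kept; no true effect; independent-groups t-test, because the arms are parallel.

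Bias = (k/25) × δ. The smallest value is (1/25) × 0.25 = 0.01 SD and the largest is (5/25) × 1 = 0.20 SD.

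Simulated two-sided type I error (400,000 trials per cell):

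| Removed of 25 | δ = 0.25 | δ = 0.5 | δ = 1 |
|---|---|---|---|
| 1 | 5.0% | 5.0% | 5.2% |
| 2 | 5.0% | 5.2% | 5.8% |
| 3 | 5.2% | 5.5% | 6.7% |
| 5 | 5.3% | 6.2% | 9.2% |

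If unfittable patients are more active instead, the error rates are the same, because a two-sided test in this model is symmetric; only the sign of the bias changes. If half of the unfittable controls are removed too, the bias with k = 5 and δ = 1 is 0.11 SD and the error 6.2%. If all are removed, the error is about 5.0%. If all 25 + 25 are analysed as allocated with complete data, it is also about 5%.

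**5. What analysing as allocated costs.** At 25 per group, 0.809 SD is detectable with 80% power (t-test). If unfitted patients gain nothing, the average effect is 0.809 × (1 − k/25).

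| Unfitted of 25 | Effect (SD) | Power, as allocated | Power, if removed |
|---|---|---|---|
| 1 | 0.777 | 76.7% | 79.2% |
| 2 | 0.744 | 73.2% | 78.2% |
| 3 | 0.712 | 69.3% | 77.2% |
| 5 | 0.647 | 61.1% | 75.0% |

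The difference is about 2.5, 5, 8 or 14 percentage points of power. It is the usual price of keeping the randomised comparison.

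**The case for a change.** The best case for acting is that a forecast can be wrong. Allocation expects unsettled soft tissue at randomisation, and Complications lists infection and skin-edge necrosis, so some shoe-arm patients who cannot be fitted in time are foreseeable. The plan does not say whether they stay, leave, are replaced or follow the control regimen. In an open trial a population chosen late could be swayed by the results, and one sentence written beforehand would settle the matter at almost no cost. The commitment to CONSORT concerns reporting and does not fix an analysis set.

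The silence is real, and such a sentence would do no harm. But the objection identifies an unwritten convention; it does not show that the design goes wrong. Harm needs several steps together: the criterion applied after allocation, actual removal, removal mainly from one arm, a sizeable share unfitted, and a large difference in activity. The documents make the first possible only on a literal reading and direct none of the rest. A separate record of the consultant's forecast would be good housekeeping, but consultants already screen on this criterion.

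**Conclusion.** No change to the plan follows. The timing is as described, and the handling of unfitted patients is left unsaid, but this is a gap that analysts fill sensibly: eligibility is judged at screening, everyone randomised is followed to 3 months, and patients are compared in the arm to which they were allocated. Done that way, with complete 3-month data, type I error stays at about 5%.

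The bias arises only under a removal that the plan does not direct. Over the assumed range it is 0.01 to 0.20 SD. Type I error exceeds about 6.2% in only two of the twelve cells examined: 6.7% with 3 of 25 removed and 9.2% with 5 of 25 removed, both at a deficit of a full SD with every comparable control kept. These sizes rest on assumed shares and deficits and on an independent-groups t-test with 25 per arm; the documents supply only the 25. An analysis that did drop unfitted shoe-arm patients would be open to criticism, but it would depart from the ordinary reading of this plan.
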